- Subjects with a SMBG FPG value meeting the lack of glycemic control criterion at any time during the pre-specified study period will be instructed to repeat FPG measurements on 2 further consecutive days. If all 3 daily values meet the relevant lack of glycemic control criterion subjects should be scheduled for a follow-up visit (within 1 5 days) to obtain a central laboratory FPG value and review of the subject's glucose meter readings. If the central laboratory FPG value meets the criterion, the subject must be rescued.
- Subjects with a central laboratory FPG value meeting the lack of glycemic control criterion at
 a pre-specified visit will be scheduled for a follow-up visit (within 3 5 days) to obtain a
 second central laboratory FPG value and review the subject's glucose meter readings. If the
 second central laboratory FPG value also meets the criterion, the subject must be rescued.
- Subjects with a central laboratory HbA1c value meeting the lack of glycemic control criterion at or following the pre-specified Week 26 visit must be rescued.

Subjects who meet rescue criteria must first complete the Rescue Visit procedures before receiving open-label rescue medication to ensure that important trial endpoint measurements are collected.

Following completion of the Rescue Visit, rescued subjects may initiate or up-titrate open-label insulin as rescue medication, at the discretion of the Investigators. Insulin should be initiated at the lowest starting dose and titrated in accordance with the approved product label in the applicable country at the discretion of the Investigator, in addition to their blinded study medication. Additional visits for titration of rescue medication should be scheduled as per the Investigator's judgment in accordance with the approved product label for that country and by the subject's

glycemic response. Rescued subjects will then continue in the study according to their original visit schedule.

Note: Rescue medication will NOT be provided by the Sponsor unless this is a local requirement.

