8.4.2.3 Exploratory Efficacy Analyses

Exploratory analyses will be performed for overall saxagliptin and overall dapagliflozin separately, by combining all low-dose and high-dose treatment groups as appropriate.

As with the primary and secondary efficacy analyses, separate models will be used for saxagliptin and dapagliflozin analyses, and each analysis will include the (common) placebo group.

Additionally, subjects belonging to the randomization strata of background therapy metformin alone with HbA1c < 7.5% at Week 26 or Week 32 will be eligible for a third randomization:

- Subjects initially randomized to the active arm will be randomized 1:1 to either discontinuing background therapy with metformin or to continuing current treatment. For subjects randomized to withdraw metformin, those receiving the low-dose will be up-titrated to the high-dose whereas those receiving the high-dose will continue on the high-dose.
- These subjects will be used to assess the effect of dapagliflozin (or saxagliptin) monotherapy versus dapagliflozin (or saxagliptin) with metformin add-on therapy. This analysis will estimate the effect of metformin on efficacy in the presence of dapagliflozin (or saxagliptin) and indicate the effects that would be lost/gained if withdrawing metformin (and using only monotherapy).
- Subjects initially randomized to the placebo arm will be randomized 1:1:1 to either discontinue metformin and switch to the dapagliflozin high-dose, or to discontinue metformin and switch to the saxagliptin high-dose, or to continue with their current treatment (placebo+metformin).
- These subjects will be used to assess the effect of dapagliflozin (or saxagliptin) monotherapy versus metformin alone at steady state.

Exploratory efficacy endpoints for short-term assessment of saxagliptin and dapagliflozin

These analyses will be conducted on the Randomized Subjects Data Set.

Comparison of the percentage of subjects who require glycemic rescue medication or discontinue the study medication due to lack of efficacy at or prior to Week 26 will be performed between overall dapagliflozin (or saxagliptin) and placebo.

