UACR, Urinary glucose	Prim	
 Start of LT period (if applicable) Date of last dose during the ST period + 1 day 	
 Week 52/ETD date + 1 day 	
 Week 52/ETD date + 1 day
Efficacy analyses				
	Prim	
 Start of LT period (if applicable) 	
 Week 56/EOS date 	
 Week 56/EOS date
HbA1c	Sens	
 Start of LT period (if applicable) Date of last dose during the ST period + 8 days First rescue intake^d 	
 Week 52/ETD date + 8 days First rescue intake^d 	
 Week 52/ETD date + 8 days First rescue intake^d
	Prim	
 Start of LT period (if applicable) 	
 Week 56/EOS date 	
 Week 56/EOS date
FPG	Sens	
 Start of LT period (if applicable) Date of last dose during the ST period + 1 day First rescue intake^d 	
 Week 52/ETD date + 1 day First rescue intake^d 	
 Week 52/ETD date + 1 day First rescue intake^d

*Prim = Primary. Sens = Sensitivity. ETD = early treatment discontinuation.

^a The earliest date should be used if multiple dates are listed.

^b When summarising AEs leading to discontinuation, no upper cut-off day windows (i.e., 4 days and 30 days from last dosing date for AEs and SAEs respectively) are applied.

^c For safety laboratory tests sensitivity analysis is used for marked laboratory abnormality summaries only.

^d Only for analyses that exclude data after rescue.

^e The randomised withdrawal period starts from either Week 32 or Week 40 depending on the visit the third randomisation occurred at.

^f These sensitivity analyses use data up to Week 32 to exclude data from the randomised withdrawal analyses.

For analyses using data up to Week 32, in cases where Week 32 visit date is missing an imputed Week 32 date will be derived using the earliest possible date of the following:

- Week 26 date (target day 183) extrapolated to estimate the Week 32 date (target day 225)
- Third randomisation date
- Next visit date after Week 32

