4.6.3.1 Observed and change from withdrawal baseline in HbA1c and FPG

Descriptive summaries of observed and change from withdrawal baseline in HbA1c and, separately, FPG for withdrawal baseline and post-withdrawal baseline visits will be provided. This analysis will include all data regardless of rescue medication initiation or adherence. No imputation will be performed.

4.6.3.2 Percentage of subjects who achieve or maintain a HbA1c level < 7% at the end of the withdrawal period

The number and percentage of subjects who achieve or maintain a HbA1c level < 7% at the end of the withdrawal period will be provided. This analysis will include all data regardless of rescue medication initiation or adherence. No imputation will be performed.

4.6.3.3 Time to glycaemic rescue medication or discontinuation of study medication due to lack of efficacy

A time-to-event analysis (where event is first use of rescue medication or discontinuation of study medication due to lack of efficacy, whichever is earlier) during the 52-week treatment period will be analysed. Date of first dose will be date of first dose in the randomised withdrawal period. Kaplan-Meier estimates will be calculated, and 95% CIs will be presented. No Kaplan-Meier plot will be presented for this analysis.

Rules for censoring are described in Section 4.1.11.

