4.6.3.4 Percentage of subjects who initiate glycaemic rescue medication

The number and percentage of subjects who require glycaemic rescue medication during the randomised withdrawal treatment period will be provided. Date of first dose will be date of first dose in the randomised withdrawal period.

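### Withdrawal-period HbA1c, FPG and HbA1c < 7% have no pre-rescue version, so values measured on rescue insulin are reported as monotherapy results

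*SAP*

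**What the plan says.** **Question.** Protocol 8.4.2.3 says that comparing withdrawn with continued metformin, among children first randomised to active drug, should "indicate the effects that would be lost/gained if withdrawing metformin (and using only monotherapy". The monotherapy objective (Protocol 1.3.4, repeated in the SAP) names change in HbA1c, change in FPG, HbA1c < 7%, and time to rescue or discontinuation.

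**Rescue.** Entry to the third randomisation requires HbA1c < 7.5% (Protocol 3.1). Under Protocol 3.7.2, children whose HbA1c meets the rescue criterion (> 8.0%) "at or following the pre-specified Week 26 visit must be rescued". Insulin is the only permitted rescue drug, but rescue without medication is possible. Rescued children stay on study drug and keep their visit schedule to Week 52.

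**Analysis.** SAP 4.6.3.1, on HbA1c and FPG, says: "This analysis will include all data regardless of rescue medication initiation or adherence. No imputation will be performed". SAP 4.6.3.2 says: "The number and percentage of subjects who achieve or maintain a HbA1c level < 7% at the end of the withdrawal period will be provided", again on all data. Table 23 has one descriptive version of each. Appendix 8.13 labels the withdrawn groups as high-dose monotherapy.

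**Rescue as an outcome.** For time to rescue or discontinuation for lack of efficacy, SAP 4.6.3.3 says: "Kaplan-Meier estimates will be calculated, and 95% CIs will be presented". SAP 4.6.3.4 says: "The number and percentage of subjects who require glycaemic rescue medication during the randomised withdrawal treatment period will be provided".

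**Unused cut-off.** In the withdrawal-period column of Table 8, the HbA1c sensitivity row stops at the earlier of "Week 52/ETD date + 8 days" and first rescue intake. The FPG row is alike, with one day in place of eight. The footnote on first rescue intake reads: "Only for analyses that exclude data after rescue". Neither 4.6.3 nor Table 23 contains such an analysis for this period.

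**The concern.** A child withdrawn from metformin at Week 32 who is above 8.0% at Week 40 can be on insulin for about 12 weeks before Week 52. That Week 52 value then describes study drug plus insulin, yet it enters the monotherapy mean and can count as achieving or maintaining HbA1c < 7%.

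If more withdrawn than continuing children are rescued, insulin pulls the two groups together, and monotherapy looks closer to combination treatment than it was. The rescue counts show that failures happened but leave the HbA1c, FPG and responder figures unchanged.

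The plan handles the same issue differently elsewhere. The Week 26 HbA1c and FPG change analyses have versions excluding post-rescue data (SAP 4.4.2.1 and the sensitivity parts of 4.5). Within the withdrawal period, the overall adverse event summary and marked laboratory abnormalities have pre-rescue versions. Glycaemic efficacy, which insulin affects most directly, does not.

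**Working it through.** The documents give no sample size, rescue rate or expected effect for the withdrawal part, so there is no planned figure to reproduce. Everything below rests on assumptions and shows scale only.

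**General formula.** Shrinkage of the mean difference = (rescue rate if withdrawn − rescue rate if continued) × insulin effect.

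- Low: (0.10 − 0.05) × 0.5 = 0.025 points
- Middle: (0.30 − 0.10) × 1.0 = 0.2 points
- High: (0.50 − 0.10) × 1.5 = 0.6 points
- Nobody rescued: 0

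**Model using the protocol's thresholds.** Entry HbA1c is normal (mean 6.8, SD 0.7), truncated below 7.5, which gives mean 6.6 and SD 0.56. Week 40 = entry + metformin loss + normal error with SD 0.7. Rescue occurs above 8.0. Week 52 = Week 40, minus the insulin effect if rescued. All children are taken as randomised at Week 32. The only inputs from the documents are 7.5 and 8.0.

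Simulation gives 5.4% of continuing children rescued. The table shows the Week 52 difference (withdrawn minus continued), with the share lost in brackets.

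| Metformin loss | Withdrawn children rescued | All data, insulin effect 0.5 | All data, insulin effect 1.0 | Post-rescue values dropped | Last pre-rescue value carried forward |
|---|---|---|---|---|---|
| 0.50 | 15.7% | 0.45 (10%) | 0.40 (21%) | 0.40 | 0.50 |
| 0.75 | 23.7% | 0.66 (12%) | 0.57 (24%) | 0.59 | 0.75 |
| 1.00 | 33.5% | 0.86 (14%) | 0.72 (28%) | 0.76 | 1.00 |

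Check of the first row at a 1.0-point insulin effect: 0.50 − 1.0 × (0.157 − 0.054) = 0.397, and 0.103 / 0.50 = 21%.

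**What the last two columns show.** Dropping post-rescue values removes the children who failed, so the difference stays attenuated. At a 0.5-point insulin effect it is further from the truth than the all-data figure. Carrying the last pre-rescue value forward recovers the full difference, but only because the model has no drift after Week 40.

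**Responders.** Inflation = rescue rate × share of rescued children below 7% at Week 52. Assumed shares give 0.10 × 0.10 = 1 percentage point up to 0.40 × 0.50 = 20 points. In the model as written, inflation is zero at insulin effects of 0.5 and 1.0, because a child above 8.0 lowered by 1.0 is still above 7.0. With extra within-child SD of 0.4 between Weeks 40 and 52, it is 1 point or less at a 0.5-point effect, about 3 to 6 points at 1.0, and about 9 to 16 points at 1.5.

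**The case against.** A reader might infer that the plan hides loss of glycaemic control after metformin is stopped. The documents do not support that. Time to rescue is a named withdrawal-period endpoint, and the same groups get Kaplan-Meier estimates with confidence intervals and a count of children rescued. Rescue insulin dose is summarised for the period (SAP 4.3.2), and the efficacy listings flag data by rescue status. SAP 4.6.3.1 also covers every post-withdrawal visit, so for children randomised at Week 32 the Week 40 value that triggers rescue is in the table, measured before insulin.

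Other limits also stand:

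- Children randomised at Week 40 have no scheduled post-withdrawal HbA1c until Week 52, and the rescue criteria stop short of that visit. Their endpoint can be affected mainly through glucose-triggered rescue, so the model overstates the effect for them.
- Rescue need not involve insulin, and continuing children can be rescued too.
- Withdrawn children on the low dose move to the high dose, so the net loss may be smaller than assumed.
- For children first randomised to placebo, the comparison is active monotherapy against placebo plus metformin. Either side may need more rescue, so the direction is not fixed.
- All-data summaries match the trial's primary estimand and are a legitimate answer to a strategy question. The protocol does not require pre-rescue versions.
- Table 8 is partly a generic grid: its ST+LT sensitivity rows for HbA1c and FPG are likewise not taken up in SAP 4.6.2.1 or Table 23.

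These points limit the size and seriousness. They do not provide a Week 52 figure for the drug alone, which is what the stated question asks for.

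**Conclusion.** The concern holds in limited form. Withdrawal-period HbA1c, FPG and HbA1c < 7% are planned only regardless of rescue. Values on rescue insulin are therefore reported under monotherapy, and the pre-rescue cut-off in Table 8 is used by no efficacy analysis of this period.

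The stronger claim, that failure of monotherapy goes unreported, is wrong. The gap concerns the meaning of the Week 52 mean and responder figures.

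For active drug without versus with metformin, the understatement is about 10% to 28% of the difference, assuming a metformin loss of 0.5 to 1.0 points and an insulin effect of 0.5 to 1.0 points. Responder inflation is near zero at a 0.5-point insulin effect and can be larger at 1.0 to 1.5 points. All are zero without rescue and smaller for children randomised at Week 40. No direction can be stated for the placebo-origin comparison.

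Severity is minor: the analyses are exploratory and descriptive, and no confirmatory result depends on them.

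**What to change.** Keep the all-data rows, labelled as including rescue, and add:

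1. In SAP 4.6.3.2 and Table 23: number and percentage with HbA1c < 7% and no rescue insulin before Week 52, counting children given rescue insulin as not maintaining on monotherapy. SAP 4.1.1 already defines rescue initiation as first rescue insulin, so rescue managed without insulin is not counted.
2. In SAP 4.6.3.1 and Table 23: HbA1c and FPG change using the Table 8 first-rescue-intake cut-off, with the last pre-rescue value carried forward under the LOCF rule in SAP 4.1.1 and the number rescued beside it. Rescue Visit measurements, which the protocol requires before rescue medication starts, help to supply that value. The LOCF rule does not impute when the first scheduled post-withdrawal value is missing, so the number left without a value should be shown.

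Do not simply set post-rescue values to missing in an analysis without imputation. At the least, reconcile the unused Table 8 rows with 4.6.3 and Table 23.

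The cost is a few descriptive rows from data and definitions already in the SAP, plus a carried-forward assumption for rescued children, which should be stated in a footnote. No rescue rule, dose or confirmatory test changes.

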4.6.3.4 Percentage of subjects who initiate glycaemic rescue medication

The number and percentage of subjects who require glycaemic rescue medication during the randomised withdrawal treatment period will be provided. Date of first dose will be date of first dose in the randomised withdrawal period.

4.7 Safety

Safety analyses will be conducted for the ST, ST+LT, and randomised withdrawal (as applicable) periods. An additional safety analysis will be provided for the post-study visit at Week 104, to summarise assessments of measures of growth and maturity by treatment group. Summaries will be based on the Treated Subjects Data Set unless otherwise stated.

The primary analyses of safety will include data regardless of rescue medication initiation, unless otherwise specified. Additional sensitivity analyses on data collected prior to rescue will be performed for AEs and laboratory marked abnormalities.

Dapagliflozin and saxagliptin will be summarised separately. Both low-dose and high-dose dapagliflozin/saxagliptin groups will be combined for dapagliflozin/saxagliptin to provide the

safety summary for overall dapagliflozin/saxagliptin compared to placebo. A common placebo group will be included in each summary.

Additional analyses will be performed during the ST+LT period to account for the randomised withdrawal design:

- Safety analyses conducted during the ST+LT period will also be conducted during the treatment period up to Week 32.
- Safety analyses conducted during the ST+LT period will also be conducted based on the treatment received at the time of the assessment to account for changes in treatment during the randomised withdrawal period (dapagliflozin/saxagliptin/placebo).
- Weighted analysis will be conducted for select safety parameters including adverse events, marked abnormal labs and ECGs using the original randomised groups to assess the effects of dapagliflozin (or saxagliptin) versus placebo on safety endpoints for subjects on background medication (i.e., excluding subjects re-randomised to withdraw from metformin).

The weight matrix denoted by W_3 is defined as follows:

$$W_3 = \text{Diag} \begin{bmatrix} \mathbf{0}_{1 \times \frac{rn}{2}} \\ \mathbf{2}_{1 \times \frac{rn}{2}} \\ \mathbf{1}_{1 \times (1-r)n} \\ \mathbf{0}_{1 \times \frac{2rn}{3}} \\ \mathbf{3}_{1 \times \frac{rn}{3}} \\ \mathbf{1}_{1 \times (1-r)n} \end{bmatrix}$$

where r is the proportion of subjects eligible for the third randomisation and n is the number of subjects within an arm.

W_3 : For the weighted analyses, dapagliflozin (or saxagliptin) subjects who went through the third randomisation and withdrew metformin will be assigned a weight of zero, and those randomised to stay on metformin will be assigned a weight of 2. All other dapagliflozin (or saxagliptin) subjects will be assigned a weight of 1. Placebo subjects randomised to withdraw metformin and switch to active treatment will be assigned a weight of 0. Placebo subjects randomised to stay on metformin will be assigned a weight of 3. All other placebo subjects will be assigned a weight of 1.

- Safety analyses will be conducted during the randomised withdrawal period using the Randomised Withdrawal Subjects Data Set.

For subjects initially randomised to the dapagliflozin (or saxagliptin) group, the subjects re-randomised to withdraw metformin will be compared to the subjects re-randomised to stay on metformin. Separate analyses will be performed for subjects respectively randomised to either dapagliflozin or saxagliptin group.

For subjects initially randomised to the placebo group, the subjects who were re-randomised to switch to dapagliflozin (or saxagliptin) monotherapy will be compared to the subjects who were re-randomised to stay on placebo with background metformin. Separate analyses will be performed respectively for subjects re-randomised to dapagliflozin and for those re-randomised to saxagliptin, using the those re-randomised to placebo as comparator.

Additional analyses (for AEs, hypoglycaemic events, and MA labs only) will also be performed to compare all subjects taking dapagliflozin (or saxagliptin) monotherapy versus those taking placebo with background metformin during the randomised withdrawal period (adding placebo subjects randomised to withdraw metformin and switched to dapagliflozin [or saxagliptin]) monotherapy to dapagliflozin (or saxagliptin) subjects randomised to withdraw metformin).

